
All patients signing informed consent must be registered in the Interactive Response Technology (IRT). Asthma and other medications and eligibility criteria will be reviewed. Patients will be instructed regarding medications to be withheld prior to visits with spirometry (which includes Visit 1) (See Section 5.5.8).

The study will include the following:

[figure not shown]
Screening Period of up to 2 weeks to assess eligibility of new patients;

Treatment Period 1—double-blind period of 52 weeks;

Treatment Period 2—single-blind period of 104 weeks;

Follow-up Period of 4 weeks, investigational and drug-free, following last dose of study drug.

Figure 3-1 Study design

Note: As information becomes available from ongoing studies, a decision to proceed with one or both doses of QAW039 in either a controlled or an open label fashion may take place during the conduct of this study.

In Treatment Period 1, patients meeting eligibility criteria will be randomized to 1 of 3 treatments (QAW039 150 mg once daily, QAW039 450 mg once daily, or placebo once daily) in an approximate ratio of 3:3:1. During Treatment Period 2, patients will continue receiving the same treatment they received in Treatment Period 1.

During Treatment Period 1, investigators, patients, and Novartis personnel monitoring the study will be blinded to study treatment. During Treatment Period 2, investigators and patients will continue to remain blinded to study treatment while Novartis personnel monitoring the study will not be blinded to treatment.

To support worldwide registration of QAW039 and to address health authority requests, there may be interim analyses of the study. Should an interim analysis occur during Treatment Period 1, Novartis personnel monitoring the study will be unblinded to study treatment; however, investigators and patients will continue to remain blinded to study treatment.

During Treatment Period 1 and Treatment Period 2, all patients will continue to receive SoC asthma therapy according to the investigator’s judgment. During Treatment Period 1 and Treatment Period 2 of this study, investigators may adjust a patient’s SoC asthma therapy according to their clinical judgment.

Clinic visits will be scheduled approximately 4 weeks after randomization, approximately 13 weeks after randomization, and then at approximately 13-week intervals during the active-treatment periods. A follow-up visit will occur approximately 4 weeks (i.e., approximately 30

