5.6.5 Early study termination by the sponsor

The study can be terminated by Novartis at any time for any reason. This may include reasons related to the benefit risk assessment of participating in the study, practical reasons, or for regulatory or medical reasons (including slow enrolment). Should this be necessary, the patient must be seen as soon as possible and treated as a prematurely withdrawn patient. The investigator may be informed of additional procedures to be followed in order to ensure that adequate consideration is given to the protection of the patient's interests. The investigator will be responsible for informing the Institutional Review Board/Independent Ethics Committee (IRBs/IECs) of the early termination of the trial.

6 Visit schedule and assessments

Patients/subjects must be seen for all visits on the designated day, or as close to it as possible. Missed or rescheduled visits should not lead to automatic discontinuation. Patients who discontinue study treatment before completing the study and accept to remain in the study will return for study visits as described in [Section 5.6.2](#). Patients who prematurely discontinue the study for any reason should be scheduled for a visit as soon as possible, at which time all of the assessments listed for the final visit will be performed. At this final visit, all dispensed investigational product should be reconciled and the adverse event and concomitant medications reconciled on the CRF.

[Table 6-1](#) lists all of the assessments and indicates with an “x” when the visits are performed.

Note that the visit schedule for the screening and randomization visits (Visit 1 and Visit 201) for patients completing a prior Phase 3 study of QAW039 will be different from the visit schedule for the screening and randomization visits for patients who have not previously participated in a study of QAW039.

- **For patients completing a prior Phase 3 study of QAW039:** the last visit in the treatment period of the prior study (e.g., Visit 299) will occur on the same day as the screening visit (Visit 1) for Study A2315. The randomization visit (Visit 201) will occur on the following day (i.e., 1 day after Visit 1) so there is no interruption of study treatment and to allow for pre-dose assessments for Study A2315.
- **For patients who have not previously participated in a study of QAW039:** the screening visit (Visit 1) will occur approximately 2 weeks before the randomization visit (Visit 201).

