2.1.1.5 Study completion and last contact

A patient will be considered to have completed the study when the patient has completed the last visit planned in the protocol.

[figure not shown]
Study completion for a patient can occur after he/she has completed 52 weeks of treatment in Treatment Period 1, or after the additional 104 weeks of treatment in optional Treatment Period 2 (total of 156 weeks of treatment) or if they have prematurely withdrawn. Completion of the study will be when all randomized patients have met the definition of study completion described above and have completed the post-treatment follow-up visit.

For all patients/subjects a safety follow-up visit (visit 401) should be conducted (e.g. by telephone) 30 days after last visit (299, Week 52 for patients not continuing into Treatment Period 2 and visit 399, week 156 for patients completing Treatment Period 2).

The maximum of the date of last visit, date of last phase completion, date of withdrawal of consent would be the date of last contact for the patient participating in the study.

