2.5 Analysis of the primary objective

2.5.1 Primary endpoint

Primary endpoints for the study are:

Treatment Period 1:

- Time-to-first treatment emergent adverse events (AEs);
- Time-to-first treatment emergent serious adverse events (SAEs); and
- Time-to-first treatment emergent AE leading to discontinuation from study treatment.

of QAW039 (150 mg once daily and 450 mg once daily), compared with placebo in patients with moderate-to-severe asthma receiving SoC asthma therapy.

Treatment Period 1 and Treatment Period 2 combined:

- Time-to-first treatment emergent adverse events (AEs);
- Time-to-first treatment emergent serious adverse events (SAEs); and
- Time-to-first treatment emergent AE leading to discontinuation from study treatment.

of QAW039 (150 mg once daily and 450 mg once daily), compared with placebo in patients with moderate-to-severe asthma receiving SoC asthma therapy.

As this study has been early terminated, the primary endpoint will be analyzed in the way of combined treatment period 1 and treatment period 2. Treatment emergent AEs are defined as adverse events (including asthma exacerbations), starting on or after the day of the first intake of study drug in this study and until the earlier date out of: date of last intake of study drug +7 days (30 days in the case of a serious AE) and final visit.

Any AEs that started during the study after informed consent and before the time of the first intake of study drug will be classified as a prior AE and not classified as treatment emergent AE. The time-to-first treatment emergent AE is defined as the time to the occurrence of an AE from the treatment start date, and computed as time to AE=AE start date – treatment start date +1 day. As a general rule of censoring, patients who either completed the study or discontinued

treatment prematurely or continued treatment and without the event of interest will be censored at the minimum out of the dates of last medication intake + 30 days, final visit date, and date of death. Time-to-first treatment emergent SAEs and time-to-first treatment emergent AEs leading to discontinuation from study treatment are defined in a similar manner as time-to-first treatment emergent AE.

The definition and rationale for the estimand for the primary endpoint are given in [Table 2-1](#). The statistical strategy to handle each intercurrent event is described in more detail in [Section 2.5.3](#).

Table 2-1 Summary of estimand for the primary endpoint

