2.8.1 Adverse events (AEs)

Adverse events after informed consent including asthma exacerbations will be recorded. Adverse events that started during the study after informed consent and before the day of the first intake of study drug will be classified as prior adverse events and not included in tabulations of treatment emergent adverse events.

The following treatment emergent AE summaries will be produced by system organ class (SOC), preferred term (PT), treatment on overall population, by source of patients for:

1. all AEs,
2. all AEs by maximum severity,
3. suspected drug-related AEs,
4. AEs by standardized MedDRA query (SMQ) level
5. SAEs, and
6. AEs leading to permanent discontinuation of study-drug.

The number of patients experiencing an event, as well as the exposure-adjusted incidence rate (patients with events per 100 patient year of follow-up) will be provided in above summaries. Patient year of follow-up will be computed as (sum of the duration of exposure over patients, in days)/365.25. This method will account for the length of follow-up time under the assumption that events would occur with the same frequency at any point in time.

Summaries described above will also be produced by source of patients.

Post-treatment discontinuation AEs (events that start more than 7 days (30 days in the case of a serious AE) after the last intake of study drug) will be summarized separately in terms of number and percentage of patients with at least one AE.

Secondary endpoint: the rate of patients with at least one treatment emergent AE by primary system organ class

The number and proportion of patients with at least one treatment emergent AE by primary system organ class will be presented descriptively and analyzed using a logistic regression model stratified by randomization stratum (but not by region) and treatment group, severity of asthma (GINA treatment step 3, 4, and 5), and region as fixed class effects. Estimates of the odds ratios between QAW039 groups and placebo will be displayed along with associated 95% confidence intervals. Firth's penalized likelihood will be utilized for logistic regression for rare events.

Secondary endpoint: the rate of treatment emergent severe asthma exacerbation episodes requiring hospitalizations

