- AEs of special interest are only presented descriptively. Time-to-first-event analyses using Kaplan-Meier plots and Cox regressions as well as incidence for recurrent events per patient year will not be presented.
- The secondary endpoint of the rate of patients with at least one treatment emergent AE by primary system organ class will be analyzed using a logistic regression model instead of a Cox regression model.
- Shift tables relative to the normal reference ranges to summarize the on-treatment change from baseline to post-baseline for each laboratory parameter or ECG parameter or vital sign assessments will not be presented.

█ [REDACTED]

[figure not shown]
- In protocol, treatment emergent adverse events (TEAEs) were defined as AEs starting on or after the time of the first intake of study drug and until the day after the last intake of study drug. This definition was updated in analysis based on clinical and safety consideration as follows: adverse events (including asthma exacerbations), starting on or after the day of the first intake of study drug in this study and until the dates of last intake of study drug +7 days (30 days in the case of a serious AE) .

█ [REDACTED]

█ [REDACTED]

- Subgroup analyses on primary outcomes are removed.

[REDACTED]

6 Appendix

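### SAP 2.5.1 closes the treatment-emergent window at an undefined 'final visit', a cap absent from SAP 4 and 2.8.1, so events soon after last dose may fall in neither adverse-event class

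*SAP*

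**What the plan says.** SAP 2.5.1 counts an AE as treatment emergent from the day of first intake until the earlier of "date of last intake of study drug +7 days (30 days in the case of a serious AE) and final visit". For patients without an event, the same section has them "censored at the minimum out of the dates of last medication intake + 30 days, final visit date, and date of death".

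SAP Section 4, which records changes from the protocol, explains that the window was lengthened on clinical and safety grounds from the protocol's one day after last intake. There it runs "until the dates of last intake of study drug +7 days (30 days in the case of a serious AE", with no visit limit.

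SAP 2.8.1 defines post-treatment AEs as "events that start more than 7 days (30 days in the case of a serious AE) after the last intake of study drug". It does not mention a final visit either.

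None of these sections gives 'final visit' a visit number. SAP 2.1.1.5 uses 'last visit' for 299 (Week 52) or 399 (Week 156) and treats the follow-up contact as separate: a "safety follow-up visit (visit 401) should be conducted (e.g. by telephone) 30 days after last visit". Protocol Section 6, on patients who leave the study early, says "At this final visit, all dispensed investigational product should be reconciled".

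**The concern.** The two AE classes should be complementary: every AE after first dose should be either treatment emergent or post-treatment. As written, one boundary depends on a visit and the other does not. If the visit comes before day 7 (or day 30 for an SAE), an event between the two boundaries meets neither definition. An SAE ten days after a completer's last dose is an example if 'final visit' is the end-of-treatment visit: it comes after the final visit, yet is not more than 30 days after last intake.

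On that reading the cap also cancels, for patients on drug at their final visit, the extension that Section 4 says was adopted. The censoring rule carries the same limit, so the primary Cox analysis of time to first SAE is affected as well as the descriptive tables. In a study whose primary and secondary objectives are all about safety, the primary SAE window would depend on which of two SAP sections a programmer follows.

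**Working it through.** No sample size or power figure in the plan depends on this window, so there is no stated figure to reproduce. The check is a reading of the terms followed by date arithmetic.

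**Which visit is the final visit?**

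- For 299/399: SAP 2.1.1.5 and Protocol 5.6.1 call these the last visit and place Visit 401 30 days later. Protocol Section 6 uses 'final visit' for the visit where drug is reconciled. SAP 2.5.1 says the study was terminated early, and Protocol 5.6.5 then treats patients as prematurely withdrawn, the group to whom that Section 6 wording applies. The SAP also has a defined term for end of observation, date of last contact, and does not use it here.
- For Visit 401: Protocol 3.2 puts the final assessment at Week 160. Protocol 5.6.1 plans Visit 401 for all patients and collects AEs there.

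The balance favours 299/399 but does not settle it.

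**Length of the gap**

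Let W be the post-dose window (7 days for AEs, 30 for SAEs) and F the days from last dose to final visit. The treatment-emergent class closes at min(W, F) and the post-treatment class opens after W, so

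gap = W − min(W, F).

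For completers, Table 6-1 schedules a witnessed dose at 299 and 399, so F = 0 on the first reading. For Visit 401, F = 30 from the text of Protocol 5.6.1 and SAP 2.1.1.5, or F = 1120 − 1092 = 28 from the Table 6-1 study days.

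| Final visit taken as | F (days) | AE gap (days) | SAE gap (days) |
|---|---|---|---|
| 299/399 | 0 | 7 − 0 = 7 | 30 − 0 = 30 |
| 401, Table 6-1 days | 28 | 7 − 7 = 0 | 30 − 28 = 2 |
| 401, 30 days after last visit | 30 | 7 − 7 = 0 | 30 − 30 = 0 |

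**Chance of a first event in the gap**

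The placebo rates per patient-year are from SAP Table 3-1: AEs 2.86 to 3.01, SAEs 0.07 (A2316/A2317 rollovers) to 0.24 (A2307/A2314 rollovers and new patients). For a patient still at risk, the probability is 1 − exp(−rate × gap/365.25).

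- AE, 7 days: 1 − exp(−2.86 × 7/365.25) = 5.3%; at 3.01, 5.6%.
- SAE, 30 days: 1 − exp(−0.07 × 30/365.25) = 0.57%; at 0.24, 1.95%.
- SAE, 2 days: at 0.07, 0.04%; at 0.24, 0.13%.

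At the plan's assumed hazard ratio of 1.5, the 30-day SAE figures become 0.86% and 2.91%.

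**After the fix**

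With one shared boundary the gap is 0 days for AEs and SAEs on either reading.

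**The case against.** The strongest reply is that 'final visit' may well mean Visit 401. Then non-serious AEs have no gap and SAEs at most 2 days on schedule, and what remains is a wording mismatch. This stands as a limit on the size of the problem. It does not remove the conflict between 2.5.1 and Section 4.

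Section 4 also says that non-treatment-emergent AEs in follow-up will be summarized separately. Read literally, that would pick up the day-10 SAE, so one cannot say that such events vanish from every table. But 2.8.1, which specifies the table, would not select them. Deaths are not lost from the report, since SAP 2.8.2 lists every death in the clinical database; what can be missed is their place in the treatment-emergent death summary and the SAE endpoint.

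Three stronger conclusions are tempting and are not supported:

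- *A count of lost SAEs.* Taking 50% to 90% of 1,570 patients as on drug at their final visit, times 1.95%, gives about 15 to 28. The documents give no basis for that share. The sum also applies the 0.24 rate to A2316/A2317 rollovers and ignores patients who have already had an SAE (about 21% after one year, 1 − exp(−0.24)).
- *Early termination puts most patients in the zero-day case.* The same-day dose is established only for completers, through the witnessed doses. The treatment discontinuation visit in Table 6-1 has none, and nothing shows how long after last dose terminated patients were seen.
- *Bias between arms.* The planning rates of 0.22 (placebo) and 0.16 (QAW039) are assumed censoring rates, not treatment-stopping rates. For SAEs the final-visit limit cuts events and risk time together, so under the independent-censoring assumption of SAP 2.5.3 the main effect is lost information.

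**Conclusion.** The point holds as an inconsistency in the definition of the primary endpoints. The visit limit is in 2.5.1 and is absent from Section 4 and from the post-treatment definition in 2.8.1, so those two classes do not cover all AEs.

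The size depends on an undefined term. On the reading the documents favour, a completer's window closes at day 0. That leaves 7 days of AEs and 30 days of SAEs in neither class, and in those 30 days about 0.6% to 2.0% of at-risk placebo patients would have a first SAE. On the Visit 401 reading the gap is 0 days for AEs and 0 to 2 days for SAEs, or at most about 0.13% of at-risk placebo patients. All percentages rest on the plan's constant-rate assumptions and are illustrative. Patients who stop drug early but stay in the study have a later final visit and are generally unaffected. No direction of bias in the hazard ratios follows from this.

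**What to change.** Three linked edits to the SAP:

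1. In 2.5.1, delete the final-visit limit from the treatment-emergent definition, so that it matches Section 4: last intake plus 7 days, or plus 30 for SAEs.
2. In the censoring rule for the SAE endpoint, replace the final visit date with date of last contact, stating that this includes Visit 401. Keep as an event any SAE recorded within 30 days of last intake, even if it starts after that contact. Without this clause, an SAE on day 29 or 30 could still be missed when Visit 401 falls on Day 1120.
3. In 2.8.1, define post-treatment AEs as all AEs after first dose that are not treatment emergent. The two classes are then complementary by construction.

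The cost is a few sentences and one date derivation. No new data are needed: Visit 401 already collects AEs, and Protocol 7.2.2 requires SAEs to be reported until 30 days after last administration.

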9.4.1 Variables

The primary variables for the study are:

- Time-to-first treatment emergent AE;
- Time-to-first treatment emergent SAE; and
- Time-to-first treatment emergent AE leading to discontinuation from study treatment.

Adverse events (including asthma exacerbations), starting on or after the time of the first intake of study drug and until the day after the last intake of study drug will be classified as treatment emergent AEs. Any AEs that started during the study after informed consent and before the time of the first intake of study drug will be classified as a prior AE and not classified as treatment emergent AE. The time-to-first treatment emergent AE will be defined as the time to the occurrence of an AE from the treatment start date, and will be computed as time to AE=AE start date-treatment start date+1 day. Treatment emergent SAEs and AEs leading to discontinuation from study treatment will be defined in a similar manner.

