9.4.3 Handling of missing values/censoring/discontinuations

Patients that do not experience a treatment emergent AE prior to study end or the day after treatment discontinuation will be considered censored at the time of study end or the day after the last intake of study drug. For the analysis of the 52-week data from Treatment Period 1, patients without a treatment emergent AE during Treatment Period 1 will be considered censored on the day after their last intake of study drug in Treatment Period 1 or on the day of the completion visit (Visit 299) in Treatment Period 1, if the patient continued into Treatment Period 2.

The primary Cox regression model will implicitly impute the censored data under the assumption of independent censoring (conditional on the baseline covariates). That is, a censored patient is assumed to be no more or less likely to experience an event in any future time interval than other patients in the same stratum that continue to be at risk for a first event and that have the same model covariates. The implied assumption of a continued treatment effect after treatment discontinuation is considered conservative for the purpose of the evaluation of safety outcomes that are assumed to be more likely to occur while active treatment is ongoing. The sensitivity analyses described in [Section 9.4.4](#) will evaluate the impact of these assumptions on the trial conclusions.

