Population		Justification	

Male or female patients aged 12 years and older with moderate-to-severe asthma on standard-of-care asthma therapy and receive at least one dose of study treatment, including two categories of patients:
 
 • Rollover patients: patients completing a prior Phase 3 study (A2307, A2314, A2316, or A2317) of fevipirant; and • New patients: patients with inadequately controlled asthma who had not previously participated in a study of fevipirant. 		
Fevipirant (QAW039) is a Prostaglandin D2 receptor 2 (DP2) antagonist expected to provide benefit in asthma by impacting major effector cells and soluble factors driving airway inflammation in asthma. Treatment with fevipirant should result in a decrease in these parameters of airway inflammation as well as a clinical improvement in asthma.
	
Variables		Justification	

 • Time-to-first treatment emergent AEs • Time-to-first treatment emergent SAEs and • Time-to-first treatment emergent AE leading to discontinuation from study treatment. 		
The primary endpoints provide safety assessments with respect to the timing of first occurrence of treatment emergent AEs, SAEs, and AEs leading to study treatment discontinuation.
	
Intercurrent event	Description	Strategy to handle event	Justification
Discontinuation of fevipirant for any reason without experiencing a safety outcome as defined in the primary variables	Discontinuation of fevipirant for any reason regardless of relation to fevipirant without experiencing a safety outcome as defined in the primary variables	A hypothetical strategy will be used assuming a continued risk for a first event after study treatment discontinuation as described in Section 2.5.3	
These patients may discontinue therapy in clinical practice. Any fevipirant treatment effect would cease almost instantly after discontinuation of fevipirant, and only SoC effect is expected.
 
The safety outcomes would be no more or less likely to occur after discontinuation of fevipirant.

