2.5.3 Handling of missing values/censoring/discontinuations

The primary Cox regression model will implicitly impute the censored data under the assumption of independent censoring (conditional on the baseline covariates). That is, a censored patient is assumed to be no more or less likely to experience an event in any future

time interval than other patients in the same stratum that continue to be at risk for a first event and that have the same model covariates. The implied assumption of a continued treatment effect after treatment discontinuation is considered conservative for the purpose of the evaluation of safety outcomes that are assumed to be more likely to occur while active treatment is ongoing.

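### For time-to-first AE leading to discontinuation, SAP 2.5.1 keeps event-free patients at risk for up to 30 days after the drug has stopped; the effect on the plan's inputs is small

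*SAP*

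**What the plan says.** SAP 2.5.1 counts an AE as treatment emergent up to the earlier of "date of last intake of study drug +7 days (30 days in the case of a serious AE) and final visit". Patients without the event of interest, whether they completed, stopped early or continued, "will be censored at the minimum out of the dates of last medication intake + 30 days, final visit date, and date of death". The same paragraph adds that "time-to-first treatment emergent AEs leading to discontinuation from study treatment are defined in a similar manner" as time-to-first AE. Neither Table 2-1, SAP 2.5.2 nor SAP 2.5.3 gives an exception for that variable.

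The protocol used one date for both purposes. An AE starting "until the day after the last intake of study drug will be classified as treatment emergent AEs" (9.4.1), and event-free patients were "censored at the time of study end or the day after the last intake of study drug" (9.4.3).

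For discontinuation of the drug, SAP Table 2-1 states: "A hypothetical strategy will be used assuming a continued risk for a first event after study treatment discontinuation". SAP 2.5.3 likens a censored patient to "other patients in the same stratum that continue to be at risk for a first event" with the same covariates.

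**The concern.** A risk set should hold only patients who could still have the event. For this variable the event is an AE that makes the patient stop the drug. Once the drug has stopped for another reason, almost nothing can qualify. The exception is an AE that starts during a permitted interruption (Protocol 5.5.5) which later becomes permanent. From day 8 a non-serious AE is also ruled out by the SAP's own window: SAP 2.8.1 treats as post-treatment those "events that start more than 7 days (30 days in the case of a serious AE) after the last intake of study drug".

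Protocol 5.6.2 asks patients who stop the drug to remain in the study, so the final-visit cap will often not remove the tail. Up to a month at almost no risk then enters as observed event-free time. This can lower the cumulative incidence curve. It also shifts the hazard ratio if the arms stop treatment at different rates.

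**Working it through.** **Inputs** (SAP section 3, Table 3-1): placebo rate 0.03 per patient-year in every stratum; hazard ratio 1.5, so 0.045 on active; censoring rates 0.22 placebo and 0.16 active; 1,570 patients at about 3:3:1, i.e. 673, 673 and 224; follow-up T of 1 or 3 years.

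**1. Reproduce the plan's power.** Expected events per arm = n·h/(h+c)·(1 − exp(−(h+c)T)).

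| T | Placebo events | Events per active arm | SE = √(1/dP + 1/dA) | Power = Φ(ln 1.5/SE − 1.96) | Plan, per dose |
|---|---|---|---|---|---|
| 1 year | 5.95 | 27.4 | 0.452 | 14.4% | 16% |
| 3 years | 14.2 | 67.8 | 0.292 | 28.4% | 29% / 28% |

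A stratified simulation with profile-likelihood intervals gives 15.9/15.2% at 1 year and 30.3/30.0% at 3 years. The inputs are therefore read as the plan intends.

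**2. Hand check of the tail.** Patients leave the drug at rate c and then stay at risk for 30/365.25 = 0.0821 years. The risk set is inflated by about 1 + c × 0.0821.

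- Placebo: 1 + 0.22 × 0.0821 = 1.018.
- Active: 1 + 0.16 × 0.0821 = 1.013.
- Hazard ratio multiplied by 1.018/1.013 ≈ 1.005, so 1.5 becomes about 1.507.
- Placebo at 3 years: 1 − exp(−0.09) = 8.61%; with the tail, 1 − exp(−0.09/1.018) = 8.46%.

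**3. Numerical solution.** Events and dropout are exponential, events occur on drug only, and the Cox score equation is solved in large samples for the 3-year case.

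| Dropout, placebo / active | HR, censored at last dose | HR, +7 days | HR, +30 days |
|---|---|---|---|
| 0.22 / 0.16 (plan) | 1.500 | 1.502 | 1.507 |
| 0.16 / 0.22 (swapped) | 1.500 | 1.498 | 1.493 |
| 0.19 / 0.19 (equal) | 1.500 | 1.500 | 1.500 |

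Three-year Kaplan-Meier on plan inputs: placebo 8.61% at last dose, 8.57% at +7 days, 8.46% at +30 days; active 12.63% at last dose and 12.48% at +30 days.

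The shift in log hazard ratio is 0.005, about 0.02 of the 3-year SE. Simulated power moves by less than one point: 15.9/15.2% to 16.1/15.5% at 1 year, and 30.3/30.0% to 30.9/30.6% at 3 years.

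**4. How far the size could move.** The scenarios below are assumptions, not figures from the documents.

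- *Fewer tails.* If half of the early stoppers leave the study at once, the hazard ratio is about 1.504.
- *More tails.* SAP 2.5.1 says the study was terminated early. Patients then come off the drug at different follow-up times, and their tails overlap other patients' time on drug. With stopping times uniform over 0-1, 0-2 or 0-3 years and a full tail for everyone, 1-year placebo incidence falls from 2.96% to 2.31%, 2.76% or 2.82%. The hazard ratio stays near 1.507.
- *Much more stopping on active.* With rates of 0.16 on placebo and 0.44 or 0.80 on active, a true 1.5 reads as about 1.47 or 1.43.

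**The case against.** The strongest reply is that the +30-day date was widened on purpose so that late serious AEs count, and that an AE leading to discontinuation can itself be serious. Visits are about 13 weeks apart (Protocol 3.1), and the drug may be interrupted for an AE. The last intake can therefore precede the recorded decision to stop, and the tail is not strictly event-free. This stands in part. The documents give no frequency for such cases. Any fix must also keep these events visible, because SAP 2.8.1 tabulates AEs leading to permanent discontinuation.

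A second reply is that the final-visit cap removes the tail. That depends on which visit is meant. Protocol section 6 uses the term for the visit at which study drug is reconciled. SAP 2.1.1.5 places follow-up Visit 401 30 days after the last visit of the treatment period. Under the first meaning many tails shrink sharply; under the second they largely remain.

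A third reply is that the shift is negligible and no formal hypothesis test is planned. That is true on the plan's inputs, and it sets the severity. It does not make the rule right for this variable.

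A reader might also infer that the SAP contradicts its own estimand. The text does not go that far. SAP 2.5.3 describes what is assumed about a patient once censored, and Table 2-1 refers to it; neither sets the censoring date. The tail fits the hypothetical strategy poorly but does not contradict its wording.

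**Conclusion.** The censoring rule is wrong as written for one primary variable, and the point is minor. The rule departs from the protocol's matched event window and censoring date. On the plan's inputs it moves the hazard ratio by about 0.5% and placebo incidence by about 1.7% in relative terms. Those sizes assume that every early stopper stays at least 30 days and that nobody gains a tail from early termination. They are therefore neither upper nor lower bounds.

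Some stronger inferences are not supported:

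- *The rule hides harm.* Under the assumed dropout the hazard ratio moves up. It moves down only if active patients stop more often, which the plan does not assume.
- *Kaplan-Meier is always pulled down.* A tail lowers the curve only where it overlaps later events, and an event counted inside the tail raises it.
- *The stated power is wrong.* It is reproduced closely, and the tail changes it by under one point.
- *The exposure-adjusted rates share the flaw.* SAP 2.8.1 divides by duration of exposure, which SAP 2.4.1 runs from first to last dose.
- *All three primary variables are wrong in the same way.* For SAEs the window and the censoring date match. For time-to-first AE a serious event can still count on days 8-30, so the mismatch is only partial.
- *The change was not declared.* The readable part of SAP section 4 lists the wider event window but not the new censoring date. Some bullets there are blacked out, so nothing follows from that.

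**What to change.** In SAP 2.5.1, add a line for time-to-first treatment emergent AE leading to discontinuation only: count events and censor event-free patients at one common date, last intake +7 days, capped at final visit and death. Keep +30 days for time-to-first SAE, and leave the TEAE definition unchanged.

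Three statements should accompany it:

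- A serious AE leading to discontinuation that starts on days 8-30 remains in the SAP 2.8.1 table and is listed separately from the Cox analysis, so that the two outputs can be reconciled.
- *Final visit* is tied to a named visit.
- The changed censoring date is listed in SAP section 4, if it is not already there.

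The cost is a few lines of text and one changed derivation, with no new data. A rare late AE that starts in an interruption which becomes permanent would drop out of the Cox analysis. The remaining distortion on plan inputs is a hazard ratio of 1.502 against 1.500, and 3-year placebo incidence of 8.57% against 8.61%.
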